Evaluating the Efficacy of Lateral Heel Wedges for Osteoarthritis of the Knee

NCT: 02254473 March 1, 2014

Evaluating the Efficacy of Lateral Heel Wedges for Osteoarthritis of the Knee

Principal Investigator: [name]

Significance

Given the prevalence of osteoarthritis of the knee and the general aging trends of the population it is important to develop effective non-operative interventions to reduce pain and improve function in the adult population with osteoarthritis (OA) of the knee. A large body of experimental evidence documents the potential for cartilage regeneration in the osteoarthritic joint under conditions of mechanical unloading of the involved joint. An easily applied, off-the-shelf shoe insert material that, when configured properly, will unload the medial compartment of the knee has been developed. The purpose of this investigation is to document the acceptability and effectiveness (with patient reported measures) of this insert compared to a control insert which does not unload the medial compartment of the knee in a group of patients with significant OA of the medial compartment of the knee in order to develop pilot data to document the effect size, acceptability of the inserts, compliance, feasibility, and power for a future clinical trial. Following communication with NIAMS officials we plan to submit an R34 proposal for this purpose. Multiple clinical trials measuring the impact of shoe inserts on knee OA symptoms report minimal benefit. These trials are conducted in a manner which used: 1. self-reported OA, 2. subjects not presenting for treatment and 3. Not in a stratified population of patients with moderate to severe medial compartment OA. Our study selects for patients with this moderate to severe medial compartment OA who pass the screening test of sufficient MCL laxity to allow correction of the weight bearing axis. Further the material used in these inserts is of a different stiffness which is molded to that of the human heel pad. This clinical trial will likely never be industry funded because of the inexpensive nature of the intervention.

Objectives and Hypothesis

Regularly wearing a 5 degree sloped insole over the course of one year will result in a wider joint space by x-ray in 60% of the subjects, a significant decrease in knee pain, decreased use of over the counter analgesics, and a clinically important 2 point improvement in the Womac pain and stiffness scale.

Methods

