We will recruit 80 adults with Kellgren-Lawrence changes between grade 2-4 medial compartment osteoarthritis of the knee from the TRIA Orthopaedic Center in Minneapolis, MN. The subjects will be randomized to a 5 degrees lateral wedge shoe insert or a flat shoe insert of similar properties through a random table generator application which will be coordinated through the TRIA Orthopaedic Center.

Inclusion Criteria:

- Adult patients 30 years or older with symptomatic medial compartment knee osteoarthritis and Grade 2-4 Kellgren-Lawrence radiographic changes presenting for treatment of knee pain.
- Range of motion knee-flexion beyond 100 degrees and not lacking more than 15 degrees of extension.
- Subtalar and forefoot motion permitting foot/ankle eversion with weight bearing.
- Sufficient shoe toe box height to allow space for the insole and therefore comfort and compliance.
- Passive laxity of medial capsule and collateral ligament by knee extension test.

Exclusion Criteria:

- All other forms of knee arthritis other than osteoarthritis.
- Bilateral symptomatic osteoarthritis of the knee.
- Knee Instability- medial pseudo-opening of greater than grade 1 or detectable anterior-posterior instability.
- Less than Grade 2 Kellgren-Lawrence radiographic changes in the medial compartment of the knee.
- Kellgren-Lawrence radiographic changes that are greater than or equal to the medial compartment in either the patellofemoral or lateral compartment.
- Inadequate knee range of motion as demonstrated on exam.
- Balance problems requiring the use of a walker or wheel chair (ambulation with aid).
- Diabetes with peripheral neuropathy.
- History of knee arthroscopy on the index knee within the past three months of study enrollment.
- History of reconstructive (ligamentous etc.) knee surgery within one year of enrollment.
- Intra-articular steroid injection or visco supplementation on the index knee within 1 month of study enrollment.
- Stiff subtalar or forefoot joints as demonstrated on clinical exam.
- Inadequate shoe toe box depth to accommodate the shoe insoles.
- Charcot joint.
- Fixed contracture of the medial capsule and/or collateral ligament as demonstrated on clinical exam.

Rationale for Inclusion:

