This group would otherwise be candidates for surgical intervention. Those with end stage osteoarthritic lesion would have biological potential for restoration of the cartilage. They would have range of motion that provided near normal gait and flexion enough to rise out of a chair. The insole fitting would accommodate the candidate's foot anatomy, any pathology and the geometry of their shoe.

Rationale for exclusion:

This criterion removes those conditions that would have potential to add conflicting data to the study and/or produce discomfort for the subject.

Statistical analysis plan:

All analyses will be done using S.A.S. (version 9.2) and two-sided p-values of less than 0.05 will be considered statistically significant. Appropriate descriptive summary statistics (including means and s.d.) and graphs (including histograms, kernel smoothed density plots, error bar plots) will be utilized to summarize Womac pain, stiffness and function in each treatment group at baseline, 6 month visit and 12 month visit. We will consider a linear regression using the generalized estimating equation (gee) approach to estimate the Womac pain, stiffness and function differences between wedge insert and flat insert groups with intention-to-treat principle. We selected gee as the primary approach as it accounts for the potential correlations among repeated measures within subjects. In addition, it has been shown the gee is more efficient compared to the two sample t-test, the paired t-test, the analysis of covariance (including treatment and baseline response as covariates), and is asymptotically equivalent to the analysis of covariance ii (including treatment, baseline response and an interaction between treatment and baseline response as covariates) 40. Missing data will be handled with multiple imputation using S.A.S. proc mi and mianalyze. Secondary outcomes will include clinical and functional outcomes with standardized knee radiographs, a validated University of Minnesota pain and acceptability scale, a medication log in terms of weekly hours of insert usage will be analyzed similarly and the Tegner Activity Scale to document any change in activity level in addition to the function addressed in the other outcomes instruments

Test Intervention:

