The subjects have end stage osteoarthritic lesions with potential for cartilage regeneration based upon the literature. Avoidance of surgery is advantageous to the patient. The material properties of the insoles are known. The durometer of the material is known which is relevant to the human plantar surface hardness. The material has an immediate memory to restore shape and depth which is a shorter interval than the human tissue on the plantar surface it is contacting. The fitting method provides the best opportunity for subject comfort and therefore compliance. The removal of the existing insoles removes a variable. The patient instruction during the fitting process; placement, removal and replacement educates them on the means of moving insoles from one shoe to the next. Insoles replacement every three months insures effectiveness of the material properties. The duration of the clinical trial is one year, a time sufficient to be compared to the time interval reported following high tibial osteotomy for cartilage to regenerate in similar lesion²²

Strengths of the proposed intervention:

The method of tailoring the insoles for anatomical and pathological customization should minimize discomfort and increase compliance. The plain film standing x-ray with measured joint space is a clear marker for change. The final MRI is a valid means of measuring cartilage volume and nature. The measurement emphasizes anatomical and pathological variables, thereby removing subjectivity. The single subjective outcome measure will be the Womac. The cost of the insert to the patient would be far less than if a custom insert was constructed into the shoe or any other form of treatment, surgery or otherwise.

C) Research Timeline

	6 months	12 months
Specific Aim 1	Regulatory Paperwork Approval, Study Orientation for staff, and patient enrollment	Patient Follow-up, data analysis, project completion

References

- 2. Bellamy N. Pain assessment in osteoarthritis: experience with the WOMAC osteoarthritis index. Seminars in Arthritis and Rheumatism. 1989;18(4, Supp. 2):14-17. PBS Record: 130

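### Entry is open to Kellgren-Lawrence grades 2-4, but the protocol describes the subjects as end-stage and as surgical candidates; the design does not support conclusions specific to those patients.

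*Combined protocol and SAP*

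**What the plan says.** All of the following comes from the combined protocol and SAP.

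- **Entry rule (Inclusion Criteria, under Methods).** Adults aged 30 or over who seek care for a painful knee are eligible if they have "symptomatic medial compartment knee osteoarthritis and Grade 2-4 Kellgren-Lawrence radiographic changes". The opening sentence of Methods gives the same grade range.
- **Lower limit (Exclusion Criteria).** "Less than Grade 2 Kellgren-Lawrence radiographic changes in the medial compartment of the knee". A grade 2 knee is therefore eligible by design.
- **Rationale for Inclusion.** "This group would otherwise be candidates for surgical intervention". The next sentence reads: "Those with end stage osteoarthritic lesion would have biological potential for restoration of the cartilage".
- **Benefits of this intervention and study design.** "The subjects have end stage osteoarthritic lesions with potential for cartilage regeneration based upon the literature". The same section counts avoiding surgery as a benefit. It also justifies the one-year duration by the time reported for cartilage to regrow in similar lesions after high tibial osteotomy.
- **Significance.** "Our study selects for patients with this moderate to severe medial compartment OA who pass the screening test of sufficient MCL laxity".

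Randomisation uses a computer-generated random table, with no stratification stated (Methods; Study Procedures). The GEE model for WOMAC names no covariate or subgroup for Kellgren-Lawrence grade (Statistical analysis plan).

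**The concern.** One entry rule carries population descriptions that do not match it. The scale as used here runs from 2 to 4, so a patient at the lowest admitted grade cannot also be described as end-stage. Nothing in the criteria asks for a surgical indication, a lesion stage or a minimum symptom score.

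The labels also carry part of the argument. The regeneration rationale and the one-year duration are tied to end-stage lesions, and the surgery-avoidance benefit presumes that surgery was otherwise in prospect. The hypothesis of a wider joint space in 60% of subjects, by contrast, has no limit by grade.

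The pilot is meant to supply the effect size and power for a definitive trial. If an estimate from a grade 2-4 mix is carried forward as an end-stage or surgical-candidate effect, the next trial could be planned for patients who were only part of this cohort. No step in the randomisation or analysis uses grade in a way that would make the mix visible.

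**Working it through.** The documents give no figure to reproduce, so the main check is textual.

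**1. Labels against criteria**

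| Description | Where | Enforced by a criterion? |
|---|---|---|
| Medial grade 2-4, symptomatic, presenting for treatment | Inclusion Criteria | Yes |
| Medial laxity | Inclusion Criteria; Significance | Yes |
| Surgical candidates (the group) | Rationale for Inclusion | No |
| End-stage lesions (those who have them) | Rationale for Inclusion | No; reads as a subset |
| End-stage lesions (the subjects) | Benefits section | No |

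The two end-stage statements also differ from each other. One is worded for a subset, the other for everyone.

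**2. What a subset conclusion would need.** N = 80 is from Methods. Assumed: 1:1 allocation, no dropout, one comparison of means, two-sided 5%, 80% power. The detectable difference in SD units is (1.96 + 0.84) × √(2/n per arm).

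- All 80, n = 40 per arm: 2.80 × √(2/40) = 0.63 SD
- Half advanced grade, n = 20: 2.80 × √(2/20) = 0.89 SD
- A quarter advanced grade, n = 10: 2.80 × √(2/10) = 1.25 SD

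Power for 0.63 SD within the subset would be about 51% at n = 20 and 29% at n = 10. The advanced-grade share is an assumption; the documents give none.

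**3. Chance imbalance in grade.** This is a separate question from the labels. It bears only on whether to stratify. Assume 40 per arm and 40% grade 2. A gap over 20 percentage points means more than 0.20 × 40 = 8 patients, so at least 9.

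- Grade 2 counts independent, X₁ and X₂ each binomial(40, 0.4): P(|X₁ − X₂| ≥ 9) = 5.2%.
- Exactly 32 of 80 grade 2, X₁ hypergeometric: the gap is |2X₁ − 32|, so X₁ ≤ 11 or X₁ ≥ 21. The probability is 2 × 0.0196 = 3.9%.

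The same two calculations give 1.7% and 1.0% at 20% grade 2, and 5.7% and 4.4% at 50%. A normal approximation without continuity correction overstates the 40% case: SD = √(0.4 × 0.6 × 2/40) = 0.110, which gives about 7%.

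**The case against.** The strongest reply is that the operative population is consistent wherever it governs conduct: grades 2-4 in the recruitment sentence and the inclusion list, with only lower grades excluded. The hypothesis and the SAP make no end-stage claim. The unqualified end-stage sentence sits in a benefits section, and the trial is a pilot. On this view the problem is one of wording and leaves the WOMAC comparison untouched. The last part stands: the comparison is not affected. The wording still matters, because the regeneration and duration arguments rest on it and the effect size is to be reused.

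Three stronger readings are tempting, and the documents do not support them.

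- **That the trial can say nothing about the patients it claims to study.** Advanced knees are eligible, and randomisation gives a valid comparison in whoever is enrolled. Only conclusions specific to end-stage or surgical patients go unsupported.
- **That the moderate-to-severe label in Significance also contradicts entry at grade 2.** The documents never map that label to grades.
- **That criticising earlier trials for lacking a stratified population conflicts with unstratified randomisation here.** In context the word means selected. The selection features named there (treatment-seeking patients, radiographic disease, laxity) are enforced by the criteria.

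It is also fair to say that chance imbalance does not bias a randomised estimate, that the documents do not show grade to predict WOMAC, and that stratifying an 80-patient pilot is good practice, not a requirement.

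**Conclusion.** The contradiction is real and unresolved. The end-stage description of all subjects and the surgical-candidate description of the group are not supported by the entry criteria, and the protocol's two end-stage statements disagree on whether they cover everyone or a subset. Inference should be limited to grade 2-4, laxity-screened patients. The pilot effect size should not go into the definitive trial under an end-stage or surgical label.

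The size of the mismatch cannot be computed, because the grade mix is unknown. If half the cohort were advanced grade, the detectable difference in that half would be 0.89 SD against 0.63 SD overall, so results by grade can only be descriptive. The 4-5% chance of a gap over 20 points rests on equal arms and 40% grade 2. It supports a cheap safeguard and does not measure the labelling problem.

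**What to change.** - Reconcile Rationale for Inclusion and the benefits section with the entry criteria, so that one population is described throughout. Which population to study is the sponsor's decision.
- Limit end-stage, regeneration and surgery-avoidance statements to the patients they fit. Describe the pilot effect size as that of the population enrolled when it is used for planning.
- Stratify the computer-generated randomisation by medial Kellgren-Lawrence grade, 2 versus 3-4. Each list must itself be balanced, for example by blocks; otherwise stratifying achieves nothing. At minimum, include baseline grade as a covariate in the WOMAC GEE model.
- Report the grade distribution by arm, and label any results by grade as descriptive.

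The cost is two randomisation lists in place of one, one model term, some rewording and a narrower population claim. No new measurement is needed, since grade is already read at screening.
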